Do you or does anyone on the research team who is determined by you to be responsible for the design, conduct or reporting of this research have any patent (sole right to make, use or sell an invention) or copyright (exclusive rights to an original work) interests related to this research protocol?

Yes No

If yes to either question above, list names of the investigator or responsible person:

The Yale University Principal Investigator, all Yale University co-investigators, and all Yale University individuals who are responsible for the design, conduct or reporting of research must have a current financial disclosure form on file with the University's Conflict of Interest Office. Yale New Haven Hospital personnel who are listed as co-investigators on a protocol with a Yale University Principal Investigator must also have a current financial disclosure form on file with the University's Conflict of Interest Office. If this has not been done, the individual(s) should follow this link to the COI Office Website to complete the form: <http://www.yale.edu/coi/>

NOTE: The requirement for maintaining a current disclosure form on file with the University's Conflict of Interest Office extends primarily to Yale University and Yale-New Haven Hospital personnel. **Whether or not they are required to maintain a disclosure form with the University's Conflict of Interest Office, all investigators and individuals deemed otherwise responsible by the PI who are listed on the protocol are required to disclose to the PI any interests that are specific to this protocol.**

SECTION II: GENERAL INFORMATION

1. **Performing Organizations:** Identify the hospital, in-patient or outpatient facility, school or other agency that will serve as the location of the research. Choose all that apply:

a. Internal Location[s] of the Study:

 Magnetic Resonance Research Center (MR-TAC)	 Yale University PET Center
 Yale Cancer Center/Clinical Trials Office (CTO)	 YCCI/Church Street Research Unit (CSRU)
 Yale Cancer Center/Smilow	 YCCI/Hospital Research Unit (HRU)
 Yale-New Haven Hospital	 YCCI/Keck Laboratories
 Cancer Data Repository/Tumor Registry	 Yale-New Haven Hospital—Saint Raphael Campus
 Specify Other Yale Location: Department of Radiology, Section of Interventional Radiology	

b. External Location[s]:

 APT Foundation, Inc.	 Haskins Laboratories
 Connecticut Mental Health Center	 John B. Pierce Laboratory, Inc.
 Clinical Neuroscience Research Unit (CNRU)	 Veterans Affairs Hospital, West Haven
 Other Locations, Specify: (Specify location(s)):	 International Research Site

c. Additional Required Documents (check all that apply):

 *YCCI-Scientific and Safety Committee (YCCI-SSC)	 N/A
 *Pediatric Protocol Review Committee (PPRC)	Approval Date:
 *YCC Protocol Review Committee (YRC-PRC)	Approval Date:
 *Dept. of Veterans Affairs, West Haven VA HSS	Approval Date:
 *Radioactive Drug Research Committee (RDRC)	Approval Date:
 YNHH-Radiation Safety Committee (YNHH-RSC)	Approval Date:
 Magnetic Resonance Research Center PRC (MRRC-PRC)	Approval Date:
 YSM/YNHH Cancer Data Repository (CaDR)	Approval Date:
 Dept. of Lab Medicine request for services or specimens form	
 Imaging on YNHH Diagnostic Radiology equipment request form (YDRCTO request) found at http://radiology.yale.edu/research/ClinTrials.aspx	

***Approval from these committees is required before final HIC approval is granted. See instructions for documents required for initial submission and approval of the protocol. Allow sufficient time for these requests. Check with the oversight body for their time requirements.**

2. **Probable Duration of Project:** State the expected duration of the project, including all follow-up and data analysis activities.

We plan to recruit patients over 3 years and follow patients for 5 years after their procedures. After initial treatment, patients will be followed every 6 months for the first two years, and then annually for the next 3 years. Interim data analysis will be performed every 6 months.

3. Research Type/Phase: (Check all that apply)**a. Study Type**

Single Center Study
 Multi-Center Study

Does the Yale PI serve as the PI of the multi-site study? Yes No

Coordinating Center/Data Management
 Other:

b. Study Phase N/A

Pilot Phase I Phase II Phase III Phase IV
 Other (Specify)

4. Area of Research: (Check all that apply) Note that these are overlapping definitions and more than one category may apply to your research protocol. Definitions for the following can be found in the instructions section 4c:

 Clinical Research: Patient-Oriented	 Clinical Research: Outcomes and Health Services
 Clinical Research: Epidemiologic and Behavioral	 Interdisciplinary Research
 Translational Research #1 ("Bench-to-Bedside")	 Community-Based Research
 Translational Research #2 ("Bedside-to-Community")	

5. Is this study a clinical trial? Yes No

NOTE the current ICMJE (International Committee of Medical Journal Editors) definition of a clinical trial: "any research study that prospectively assigns human participants or groups of humans to one or more health-related interventions to evaluate the effects on health outcomes." Health-related interventions include any intervention used to modify a biomedical or health-related outcome (for example, drugs, surgical procedures, devices, behavioral treatments, dietary interventions, and process-of-care changes). Health outcomes include any biomedical or health-related measures obtained in patients or participants, including pharmacokinetic measures and adverse events"

If yes, where is it registered?

Clinical Trials.gov registry
Other (Specify)

Registration of clinical trials at their initiation is required by the FDA, NIH and by the ICMJE.

If this study is registered on clinicaltrials.gov, there is new language in the consent form and compound authorization that should be used.

For more information on registering clinical trials, including whether your trial must be registered, see the YCCI webpage, <http://ycci.yale.edu/researchers/ors/registerstudy.aspx> or contact YCCI at [contact])

6. Does the Clinical Trials Agreement (CTA) require compliance with ICH GCP (E6)?

Yes No

7. Will this study have a billable service? A Billable Service is defined as a service or procedure that will be ordered, performed or result in charging in EPIC for individuals who are enrolled in a clinical research study, regardless if the charge is intended to be paid by the subject/their insurance or the research study.

Yes No

If you answered "yes", this study will need to be set up in OnCore Support

<http://medicine.yale.edu/ymg/systems/ppm/index.aspx>

8. Are there any procedures involved in this protocol that will be performed at YNHH or one of its affiliated entities? Yes No *If Yes, please answer questions a through c and note instructions below. If No, proceed to Section III.*

- a. Does your YNHH privilege delineation currently include the **specific procedure** that you will perform? Yes. [name], from Interventional Radiology, will perform the interventional radiology procedures. Percutaneous ethanol ablation of a variety of targets is within the scope of interventional radiology practice. Drs. [name], [name], [name] and [name] will perform the surgical procedures. Total thyroidectomy with central neck dissection is a routine procedure in an endocrine surgery practice.
- b. Will you be using any new equipment or equipment that you have not used in the past for this procedure? No.
- c. Will a novel approach using existing equipment be applied?
No. Percutaneous ethanol ablation is a well-established method for management of recurrent thyroid cancer nodal metastasis in patients that are not amenable to surgery. It is also a recognized treatment modality in patients with certain benign thyroid nodules.

If you answered "no" to question 8a, or "yes" to question 8b or c, please contact the YNHH Department of Physician Services ([name]) for prior approval before commencing with your research protocol.

SECTION III: FUNDING, RESEARCH TEAM AND TRAINING

1. Funding Source: Indicate all of the funding source(s) for this study. Check all boxes that apply.

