Formal cancer restaging for patients will take place every 6 months for the first two years and then annually for the following 3 years. These clinic visits will include a thorough clinical examination, surveillance ultrasonography of the neck (thyroid bed, central and bilateral lateral neck lymph nodes), laboratory tests (TSH, free T4, Tg, TgAb), quality of life assessment, pain assessment, voice assessment, symptom assessment, and cosmesis assessment.

Disease progression based on radiographic images utilizing the RECIST (Response Evaluation Criteria in Solid Tumors) criteria will result in recommendation to patient for total thyroidectomy. Disease progression is defined by $\geq 20\%$ increase of diameter of any residual visible tumor, a $\geq 5\text{mm}$ absolute increase in size of any residual visible tumor, appearance of new metastasis to central or lateral neck lymph nodes by ultrasound and FNA biopsy, or appearance of new distant metastases [53].

Duration of Project and Follow Up

Patients will be recruited over 3 years and followed for 5 years after the procedure. After initial treatment, patients will be followed every 6 months for the first two years, and then annually for the next 3 years. The data will be analyzed on an annual basis.

References:

1. Miccoli, P., et al., The impact of thyroidectomy on psychiatric symptoms and quality of life. *J Endocrinol Invest*, 2007. 30(10): p. 853-9.
2. Adler, J.T., et al., Preserving function and quality of life after thyroid and parathyroid surgery. *Lancet Oncol*, 2008. 9(11): p. 1069-75.
3. Weber, T., et al., Effect of parathyroidectomy on quality of life and neuropsychological symptoms in primary hyperparathyroidism. *World J Surg*, 2007. 31(6): p. 1202-9.
4. Cohen, S.M., et al., Creation and validation of the Singing Voice Handicap Index. *Ann Otol Rhinol Laryngol*, 2007. 116(6): p. 402-6.
5. Jacobson, B.H., The Voice Handicap Index (VHI): Development and Validation. *American Journal of Speech-Language Pathology*, 1997. 6: p. 66-70.
6. Jung, S.P., et al., A New Subfascial Approach in Open Thyroidectomy: Efficacy for Postoperative Voice, Sensory, and Swallowing Symptoms. A Randomized Controlled Study. *Ann Surg Oncol*, 2013.
7. Keller, S., et al., Validity of the brief pain inventory for use in documenting the outcomes of patients with noncancer pain. *Clin J Pain*, 2004. 20(5): p. 309-18.

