All Co-Investigators listed on the protocol.
Yale Cancer Center Data and Safety Monitoring Committee (DSMC)
National Institutes of Health
Food and Drug Administration (Physician-Sponsored IND # _____)
Medical Research Foundation (Grant _____)

The principal investigator [name] will conduct a review of all adverse events upon completion of every study subject. The principal investigator will evaluate the frequency and severity of the adverse events and determine if modifications to the protocol or consent form are required.

12. Statistical Considerations: Describe the statistical analyses that support the study design.

The Yale Center for Analytical Science was consulted to assist with statistics and will contribute to this study ([name]).

The primary aim of this study is to evaluate the effect of PEA on patient-related outcomes. The primary endpoint will be symptom assessment using the Thyroid Symptom Questionnaire (TSQ)

at the patient's 12-month visit. In addition, quality of life assessment (QOL) using SF36, pain assessment using BPI and voice assessment using VHI will be performed.

A secondary aim of this study is to evaluate the safety and feasibility of using PEA to treat primary PTMC. Consequently, we will monitor potential adverse events at the first clinic visit, including dysphonia, thyrotoxicosis, fever, hematoma, and skin necrosis. By analyzing these variables, the study team hopes to evaluate the safety and feasibility of this treatment modality.

Given the excellent prognosis of patients with PTMC (100% 5-yr survival), we do not expect any death events, progression, and recurrence related to the procedure in a feasible follow-up period. Therefore, the oncologic outcomes, including disease-free interval and overall survival (up to 5-yr follow-up), will be collected but will only serve as exploratory endpoints, evaluated at 5-year follow-up.

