Descriptive statistics, including mean and standard deviation for continuous variables and frequency and percentage for categorical variables, will be used to summarize patient characteristics. The adverse events will be investigated in order to assess the safety of the new procedure. The primary analysis will be comparing the pre-operative TSQ score to the post-operative TSQ score. Using standard deviation of 6.38 as reported in the DEPTH (DEPression and THyroid) study [54], the sample size of 16 achieves 90% power to detect a difference of 5.65 between pre- and post-PEA with a type I error of 0.05 using a paired t-test. This effect size is equivalent to one-level difference in responses for 6 items (such as from "Much worse" to "Little worse"), or three-level differences in responses for 2 items (such as from "Much worse" to "Much better"), etc.

Similarly, a power analysis was performed for QOL. The Physical Component and Mental Component of SF-36 will be used. The standard deviations, 9.7 and 11.0 for patients with thyroid disease, respectively, were used to estimate statistical power. The sample size of 16 in each group achieves 90% power to detect a difference of 8.6 in SF-36 Physical Component summary score and 9.8 in Mental Component summary score between the PEA and thyroidectomy groups with a type I error of 0.05.

Time and motion studies and a cost analysis will also be conducted.

SECTION VI: RESEARCH INVOLVING DRUGS, BIOLOGICS, RADIOTRACERS, PLACEBOS AND DEVICES

If this section (or one of its parts, A or B) is not applicable, state N/A and delete the rest of the section.

A. DRUGS, BIOLOGICS and RADIOTRACERS

1. Identification of Drug, Biologic or Radiotracer: What is (are) the **name(s)** of the drug(s) biologic(s) or radiotracer(s) being used? Identify whether FDA approval has been granted and for what indication(s).

Percutaneous ethanol injection is approved by the FDA and is a well-accepted treatment modality for the management of metastatic thyroid carcinoma to the neck, as well as benign thyroid cysts or autonomic nodules [27, 28, 30-32, 36, 55]. The injection of ethanol has been also used successfully in the cure of liver tumors [56-61].

1. Hay, I.D. and J.W. Charboneau, The coming of age of ultrasound-guided percutaneous ethanol ablation of selected neck nodal metastases in well-differentiated thyroid carcinoma. *J Clin Endocrinol Metab*, 2011. 96(9): p. 2717-20.

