Stores the investigational device according to the manufacturer's recommendations with respect to temperature, humidity, lighting, and other environmental considerations:

Ensures that the device is stored in a secure area with limited access in accordance with applicable regulatory requirements:

Distributes the investigational device to subjects enrolled in the IRB-approved protocol:

SECTION VII: RECRUITMENT/CONSENT AND ASSENT PROCEDURES**1. Targeted Enrollment: Give the number of subjects:**

- a. Targeted for enrollment at Yale for this protocol: 40
- b. If this is a multi-site study, give the total number of subjects targeted across all sites
N/A

2. Indicate recruitment methods below. Attach copies of any recruitment materials that will be used.

 Flyers	 Internet/Web Postings	 Radio
 Posters	 Mass E-mail Solicitation	 Telephone
 Letter	 Departmental/Center Website	 Television
 Medical Record Review	 Departmental/Center Research Boards	 Newspaper
 Departmental/Center Newsletters	 Web-Based Clinical Trial Registries	
 YCCI Recruitment database	 Clinicaltrials.gov Registry (do not send materials to HIC)	
 Other (describe): Patients who meet eligibility criteria will be approached by an attending surgeon at Yale Endocrine Surgery and will be asked about their interest in enrollment into the study.		

3. Recruitment Procedures:

- a. Describe how potential subjects will be identified.

A letter will be sent to referring endocrinologists to raise awareness for this clinical trial. This letter will inform the endocrinologists about the general study purpose, study design, and potential inclusion and exclusion criteria. All potential patients will be referred to Yale Endocrine Surgery for final assessment of eligibility. We include a copy of this letter with the amendment form.

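### Do the conflicting analysis schedules (6-monthly in Section II.2, annual in Section V.3) leave the primary TSQ test undefined?

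*Combined protocol and SAP*

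**What the plan says.** Section II.2 (Probable Duration of Project) describes three years of recruitment and five years of follow-up, and ends: "Interim data analysis will be performed every 6 months". Section V.3, under Duration of Project and Follow Up, gives the same timetable ("Patients will be recruited over 3 years and followed for 5 years after the procedure") but ends: "The data will be analyzed on an annual basis". Neither sentence says which data are analysed or for what purpose.

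Section V.12 (Statistical Considerations) makes the TSQ at the 12-month visit the primary endpoint and states: "The primary analysis will be comparing the pre-operative TSQ score to the post-operative TSQ score". The test is a paired t-test with type I error 0.05, and "the sample size of 16 achieves 90% power to detect a difference of 5.65 between pre- and post-PEA". The section describes no interim analysis, no division of the 0.05 and no efficacy stopping rule. It does give a time for the oncologic outcomes, which "will be collected but will only serve as exploratory endpoints, evaluated at 5-year follow-up". Section VII.1 has a different patient number: "Targeted for enrollment at Yale for this protocol: 40".

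Two other periodic activities appear in Section V.11: a review by the principal investigator at least every six months, and yearly progress reports to the Human Investigation Committee.

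**The concern.** Two near-identical paragraphs end with different analysis frequencies, and the statistical section does not say which holds. The 12-month visit fixes when each patient is measured. It does not fix when the study makes the comparison. The exploratory outcomes have a stated time and the primary one does not, which looks like the wrong way round.

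Two things could be at stake. If the TSQ were tested at every scheduled analysis at an unadjusted 0.05, the type I error would exceed 0.05. If it were tested once but at a cut chosen later, the data set, the confidence interval and perhaps the conclusion would depend on that choice. The 6-monthly schedule offers more cuts than the annual one.

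**Working it through.** **Inputs.** Recruitment over 36 months (Sections II.2 and V.3). Endpoint at 12 months, SD 6.38, difference 5.65, type I error 0.05, n = 16 (Section V.12). Enrollment target 40 (Section VII.1). Assumptions not in the documents: uniform accrual, no dropout, a two-sided test, and 6.38 taken as the SD of the change score.

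**1. The plan's own figure.** Paired t-test, n = 16, df = 15, noncentrality 5.65/6.38 × √16 = 3.54. Power is 91.1%, and 16 is the smallest n that reaches 90%. The stated 90% reproduces as a single test at the full 0.05, with nothing set aside for earlier looks.

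**2. Patients with a 12-month TSQ at month m.** n(m) = N × (m − 12)/36. The last 12-month visit falls at month 36 + 12 = 48.

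| Month | N = 16 | N = 40 |
|---|---|---|
| 30 | 8.0 | 20.0 |
| 36 | 10.7 | 26.7 |
| 42 | 13.3 | 33.3 |
| 48 | 16 | 40 |

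With N = 16, the number in the power statement, neither schedule has 16 evaluable patients before month 48. Only with N = 40 do earlier cuts pass 16: months 30, 36 and 42 on the 6-monthly schedule, and month 36 on the annual one. That count of three against one takes 40 from Section VII.1 and treats the 16 of Section V.12 as a trigger for analysis. Section V.12 gives 16 as a sample size, and no section makes it a trigger. Month 36 lies in both schedules, so nothing that happens there comes from the conflict.

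**3. Precision, if an earlier cut were used.** The 95% half-width is t(0.975, n − 1) × 6.38/√n.
- n = 20: 2.093 × 6.38/√20 = 2.99
- n = 40: 2.023 × 6.38/√40 = 2.04

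**4. Would the conclusion change?** Simulation of 200,000 trials with normal change scores, comparing the test at n = 20 (month 30) with the test at n = 40 (month 48):
- True change 5.65: the two disagree in about 4% of trials, essentially always because the smaller sample misses an effect that the full sample detects.
- True change 2.825 (half the planned effect): they disagree in about 36%. About 33 of those 36 points are not significant at n = 20 and significant at n = 40; about 2 points go the other way. Power is 47% at n = 20 and 78% at n = 40.

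The 36% is therefore mainly the loss of power from halving the sample. It is not a tendency of early cuts to give a favourable result.

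**5. Type I error.** One test after all 12-month visits: simulated 0.051 at n = 16 and 0.049 at n = 40. If the TSQ were tested unadjusted at every scheduled analysis up to month 48, the error would be about 0.18 (n = 16) or 0.16 (n = 40) on the 6-monthly schedule, and about 0.11 on the annual one. These figures show what repeated testing would cost. No section of the protocol provides for it.

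**The case for a change.** The strongest case for acting is that the protocol does schedule repeated analyses, calls one set interim, and never says that the TSQ is left out of them. The form item that Section II.2 answers asks about data analysis activities, so its sentence is not idle. A single final test is the natural reading, but it is not written down. The 6-monthly sentence may be the safety review of Section V.11 and the annual sentence the yearly committee report, but that is inference too. One sentence would settle the matter at almost no cost.

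Part of this stands. The two sentences conflict, nothing reconciles them, and the calendar time of the primary test is not stated. What does not stand is the step from there to an open primary result. Section V.12 is written as a fixed-sample design throughout, and its power figure reproduces only as one test at the full 0.05. To reach a different result an analyst would have to add an interim TSQ test, or stop at a partial data set, and the plan provides for neither. The disagreement between 16 and 40 patients, on which the larger figures depend, is a separate matter.

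**Conclusion.** This is a clerical mismatch between an administrative duration item and a summary paragraph, together with a missing detail that analysts would fill in the obvious way. Following Section V.12 gives one paired t-test of 12-month TSQ against baseline, with type I error 0.05 and, at n = 16, power of 91.1%. Neither figure depends on whether the periodic analyses are 6-monthly or annual. Reconciling the sentences would be good housekeeping, but it would alter no visit, sample size, test or result, so no change to the plan is needed.

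This conclusion rests on reading Section V.12 as a single test on the complete 12-month data. It would be different if the TSQ were in fact to be tested at the periodic analyses, which no section says. The numbers assume uniform accrual, no dropout, a two-sided test and 6.38 as the SD of the change.

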As Chair, do you have any real or apparent protocol-specific conflict of interest between yourself and the sponsor of the research project, or its competitor or any interest in any intervention and/or method tested in the project that might compromise this research project?

Yes (provide a description of that interest in a separate letter addressed to the HIC)
 No

I assure the HIC that the principal investigator and all members of the research team are qualified by education, training, licensure and/or experience to assume participation in the conduct of this research trial. I also assure that the principal investigator has departmental support and sufficient resources to conduct this trial appropriately.

[name], MBA
Chair Name (PRINT) and Signature

Date

Department: Department of Surgery

YNHH Human Subjects Protection Administrator Assurance Statement

Required when the study is conducted solely at YNHH by YNHH health care providers.

As Human Subject Protection Administrator (HSPA) for YNHH, I certify that:

- I have read a copy of the protocol and approve it being conducted at YNHH.
- I agree to notify the IRB if I am aware of any real or apparent institutional conflict of interest.
- The principal investigator of this study is qualified to serve as P.I. and has the support of the hospital for this research project.

YNHH HSPA Name (PRINT) and Signature _____

Date _____

For HIC Use Only

Date Approved _____

Human Investigation Committee Signature _____

This protocol is valid through _____

SECTION V: RESEARCH PLAN

1. **Statement of Purpose:** State the scientific aim(s) of the study, or the hypotheses to be tested.

Primary Objectives

The primary objective of the study is to determine the effect of percutaneous ethanol ablation on:

- a) Quality of life, through the SF-36 form
- b) Thyroid-related symptoms, through the Thyroid Symptom Questionnaire (TSQ)
- c) Pain (BPI), voice (VHI) and cosmesis (POSAS)
- d) Reduction and/or elimination of size of primary thyroid microcarcinoma

Secondary Objectives

A secondary objective of the study is to confirm the safety, feasibility, and cost of treating primary papillary thyroid microcarcinoma with percutaneous ethanol ablation.

Another secondary objective of the study is the assessment of oncologic outcomes, including disease-free survival and overall survival (exploratory endpoints).

2. **Background:** Describe the background information that led to the plan for this project. Provide references to support the expectation of obtaining useful scientific data.

Papillary thyroid cancer (PTC) is the most common endocrine malignancy. It is estimated that approximately 60,220 people in the United States will be diagnosed with thyroid cancer in 2013 [1]. The incidence of PTC has risen more rapidly over the past decades than that of any other malignancy (annual incidence rate in 1990: 5.50 per 100,000; in 2010: 13.83 per 100,000) [2, 3]. One reason for the increasing incidence of PTC is the widespread availability and use of high-resolution neck ultrasonography; more PTCs are being diagnosed than previously because patients are undergoing diagnostic studies.

However, an actual increase of incidence of PTC has also been documented [3]. The largest contributing factor to the rising incidence of PTC is the diagnosis of papillary thyroid microcarcinomas (PTMC) [4, 5]. The World Health Organization (WHO) defines PTMC as a papillary thyroid cancer measuring 10 mm or less in greatest dimension [6]. Because the prognosis of patients with PTC is generally very favorable, even when the tumor is diagnosed at a larger size, there is considerable debate regarding the optimal management of PTMCs that are often incidentally discovered. Clinicians must balance the overall very low morbidity of PTMCs with the potential morbidity of treatment.

PTMCs are actually very common: autopsy studies have demonstrated that up to 35.6% of people who have died from other causes are found to have occult thyroid cancer at autopsy [7-9]. The vast majority of these cancers remain silent throughout a patient's lifetime. Since PTMCs are indolent tumors that may never progress to a clinically significant degree, clinicians have begun to question whether they can be treated with less than the currently accepted standard of care for localized PTC per American Thyroid Association guidelines: total thyroidectomy (with or without central neck lymph node dissection) or thyroid lobectomy in select situations.

The morbidity of thyroidectomy is largely related to the surgical procedure. Total thyroidectomy is associated with a recurrent laryngeal nerve injury in 1.1-2.1% and permanent hypoparathyroidism with lifelong dependence on calcium in 1.5-2.9% of patients [10-13]. The cognitive and psychological consequences after thyroidectomy can also be a challenge in the post-operative period, despite adequate thyroid hormone replacement [14-19]. Although thyroid hormone replacement is effective in the majority of patients, a substantial proportion remain symptomatic and fail to regain a normal sense of well-being [17]. A case-control study in the United Kingdom showed that post-surgical patients on levothyroxine (T4) replacement displayed significant impairment in their psychological well-being, even with a normal TSH [20]. Furthermore, 34.4% of the patients who underwent a total thyroidectomy and had a recent normal TSH stated that they were dissatisfied with their overall health status [20]. Additional studies have shown that combination replacement with levothyroxine (T4) and liothyronine (T3) therapy did not improve mood and cognitive performance compared to standard T4 monotherapy [21-23].

Some centers currently recommend thyroid lobectomy alone, instead of total thyroidectomy, for patients with small, well-differentiated PTCs. In a retrospective analysis of 889 patients, Nixon and colleagues from Memorial Sloan-Kettering Cancer Center compared the outcomes of patients undergoing thyroid lobectomy versus total thyroidectomy for small, well-differentiated PTCs and found no significant differences between both groups. The extent of surgery had no effect on overall survival or locoregional recurrence rates. Notably, those patients who underwent thyroid lobectomy were not followed with serum thyroglobulin levels or annual ultrasonography, which is routinely done for patients who have undergone total thyroidectomy; therefore, it is possible that some locoregional recurrences were

not detected in the thyroid lobectomy group. The authors concluded that patients with small, well-differentiated PTCs could be safely managed with thyroid lobectomy alone [24].

A center in Japan has gone one step further by managing select patients with PTMC using observation alone. Ito and colleagues hypothesized that most PTMCs do not require immediate surgery, and therefore, they began an observational trial in 1993 [25]. Patients who were diagnosed with PTC measuring less than 1 cm were offered two options: observation without surgery or standard surgical treatment. The observation group was followed to determine whether the tumor size had changed or whether lymph node metastasis had developed. Patients with progressive disease subsequently underwent standard surgical therapy. The authors compared the outcomes of 340 patients who underwent observation and 1055 patients who underwent immediate surgery. In the observation group, 109 patients eventually underwent surgical treatment, but 231 patients (68%) continue to be observed after more than 20 years of follow-up. The authors concluded that observation is safe in select patients with PTMCs in the absence of unfavorable tumor features, and in the event of disease progression, patients can undergo surgery without a clinically significant difference in outcome.

Although thyroid lobectomy and observation are less invasive than total thyroidectomy, thyroid lobectomy is still associated with risks, and many patients and healthcare providers are uncomfortable with simple observation when cancer is involved. Therefore, neither thyroid lobectomy nor observation seems to strike the ideal balance in the treatment of PTMC. Percutaneous ablative therapy may accomplish this goal.

Percutaneous ethanol ablation has not previously been used as a treatment for primary PTC, but has been shown to be an effective treatment for recurrent PTC in patients who are not candidates for surgery for various reasons (medical comorbidity, unacceptably high risk of complications due to extensive prior surgery or radiation) [26-29]. Percutaneous ethanol ablation has successfully treated known metastatic lymphadenopathy from PTC as measured by decreased tumor volume and blood flow to the nodal metastases [27].

Heilo and colleagues from the Mayo Clinic evaluated the efficacy of percutaneous ethanol ablation in the treatment of patients with PTC metastatic to a limited number of cervical lymph nodes. Their retrospective review included 63 patients with PTC and 109

cervical lymph nodes with metastasis. Mean observation time was 38.4 months (range 3 to 72 months). A total of 101 of the 109 (93%) metastatic lymph nodes responded to percutaneous ethanol ablation, 92 with a complete response and 9 with a partial response. Two lymph nodes did not respond, and four lymph nodes demonstrated progressive disease. Two lymph nodes previously considered successfully treated showed evidence of recurrent malignancy during follow-up [28].

Percutaneous ethanol ablation has also been performed for benign thyroid disease, such as focal and diffuse autonomy of the thyroid, benign nodules, and cystic lesions. This procedure has not gained widespread acceptance, although there is accumulating evidence of the efficacy and safety of this therapeutic tool. [30-32]. Livraghi and colleagues first proposed percutaneous ethanol ablation in 1990 as an alternative novel therapeutic tool for the treatment of autonomously functioning thyroid nodules (AFTN) [31]. Other centers subsequently published small series and case reports describing successful percutaneous ethanol ablation of amiodarone-induced thyrotoxicosis, AFTN in pregnancy, and large AFTNs (nodule volume > 40 mL) [33] [34] [35-37]. Importantly, when surgery is subsequently necessary in patients who have undergone percutaneous ethanol ablation of benign thyroid nodules, surgical resection remains feasible and does not appear to carry increased risk due to scarring [38].

Percutaneous ethanol ablation of benign thyroid disease is generally well tolerated. A very common adverse effect is transient pain at the injection site. Additional transient adverse effects include dysphonia in 3.9%, worsening of thyrotoxicosis in 1.1%, self-limited fever in 5% and hematoma in 1.8% [37, 39]. There exists a single case report from Germany describing severe ethyl toxic necrosis of the larynx and overlying skin in a patient who previously underwent ethanol instillation as a treatment for an AFTN. The patient almost immediately developed aphonia and severe odynophagia, and was admitted to the hospital for eleven days. Topical ointment, intravenous and inhaled steroids, and intravenous antibiotics were administered. The patient did not require invasive therapy in the acute setting, and the voice returned to near normal within 2 weeks. Follow-up ultrasound several months after the procedure demonstrated that the target nodule was essentially unchanged, suggesting that the majority of the instilled ethanol was actually injected into the subcutaneous tissue and larynx instead of into the thyroid. Six months after the initial procedure, follow-up

laryngoscopy demonstrated that a right false vocal fold cyst had developed; this was successfully resected endoscopically ten months after the initial procedure [30].

In summary, the rising incidence of PTMC in asymptomatic patients is real, and there is no indication that this trend is beginning to plateau. Standard surgical therapy, even if limited to thyroid lobectomy, may be considered over-treatment of patients with PTMCs. Although observation alone may be sufficient for some patients, it may be preferable to treat the cancer in lieu of observation. A minimally-invasive technique such as percutaneous ethanol ablation may strike a balance between the low overall risk of PTMC and the minimal morbidity of this treatment. Percutaneous ethanol ablation has not been reported to have been used for primary thyroid cancers, but has been used to successfully treat benign thyroid disease as well as PTC recurrences and metastatic lymph nodes. Percutaneous ethanol ablation may prove to be a safe alternative to either surgical intervention or observation for patients with PTMC.

References:

1. Howlader, N.N., AM, SEER cancer Statistics Review. 2013.
2. Pacini, F., Management of papillary thyroid microcarcinoma: primum non nocere! J Clin Endocrinol Metab, 2013. 98(4): p. 1391-3.
